8.3.4 Safety Assessments and Use of the eVRC

All participants will be observed for at least 30 minutes after each vaccination for any immediate reactions. If any immediate AEs are observed during this period, the time at which the event occurred within this timeframe, as well as the event itself, any concomitant medications that were administered, and resolution of the event must be recorded on the appropriate eCRF.

Participants will use the eVRC (Section 8.1.9) to document the following information:

- Oral body temperatures measured Day 1 (day of vaccination) through Day 5 postvaccination
- Solicited injection-site AEs (redness/erythema, swelling, and tenderness/pain) Day 1 through Day 5 postvaccination
- Solicited systemic AEs (muscle pain/myalgia, joint pain/arthralgia, headache, and tiredness/fatigue) Day 1 through Day 14 postvaccination
- Any other injection-site or systemic AEs Day 1 through Day 14 postvaccination
- Concomitant medications and nonstudy vaccinations Day 1 to Day 14 postvaccination

8.3.5 Clinical Laboratory Assessments

Refer to Appendix 2 for the list of clinical laboratory tests to be performed and to the SoA for the timing and frequency.

- All protocol-required laboratory assessments, as defined in Appendix 2, must be conducted in accordance with Section 1.3.
- If laboratory values from nonprotocol-specified laboratory assessments performed at the institution's local laboratory require a change in study participant management or are considered clinically significant by the investigator (eg, SAE or AE or dose modification), then the results must be recorded in the appropriate CRF (eg, SLAB).
- For any laboratory tests with values considered clinically significantly abnormal during participation in the study, every attempt should be made to perform repeat assessments until the values return to normal or baseline or if a new baseline is established as determined by the investigator.

8.4 Adverse Events (AEs), Serious Adverse Events (SAEs), and Other Reportable Safety Events

The definitions of an AE or SAE, as well as the method of recording, evaluating, and assessing causality of AE and SAE and the procedures for completing and transmitting AE, SAE, and other reportable safety event reports can be found in Appendix 3.

Adverse events, SAEs, and other reportable safety events will be reported by the participant (or, when appropriate, by a caregiver or surrogate).

The investigator and any designees are responsible for detecting, documenting, and reporting events that meet the definition of an AE or SAE as well as other reportable safety events. Investigators remain responsible for following up AEs, SAEs, and other reportable safety events for outcome according to Section 8.4.3.

The investigator, who is a qualified physician, will assess events that meet the definition of an AE or SAE as well as other reportable safety events with respect to seriousness, intensity/toxicity and causality.

8.4.1 Time Period and Frequency for Collecting AE, SAE, and Other Reportable Safety Event Information

All AEs, SAEs, and other reportable safety events that occur after the consent form is signed but before allocation/randomization must be reported by the investigator if they cause the participant to be excluded from the study, or are the result of a protocol-specified intervention, including but not limited to washout or discontinuation of usual therapy, diet, placebo treatment, or a procedure.

All AEs, SAEs, and other reportable safety events must be reported by the investigator from the day of allocation/randomization to the first vaccination and from the day of each vaccination through 14 days postvaccination. SAEs must also be reported throughout the duration of the individual's participation in the study, regardless of whether or not related to the Sponsor's product.

Additionally, any SAE brought to the attention of an investigator at any time outside of the time period specified in the previous paragraph also must be reported immediately to the Sponsor if the event is either:

1. A death that occurs prior to the participant completing the study.

OR

2. An SAE that is considered by an investigator who is a qualified physician to be vaccine-related.

Investigators are not obligated to actively seek AEs or SAEs or other reportable safety events in former study participants. However, if the investigator learns of any SAE, including a death, at any time after a participant has been discharged from the study, and he/she considers the event to be reasonably related to the study intervention or study participation, the investigator must promptly notify the Sponsor.

All initial and follow-up AEs, SAEs, and other reportable safety events will be recorded and reported to the Sponsor or designee within the time frames as indicated in [Table 3](#).

Table 3 Reporting Time Periods and Time Frames for Adverse Events and Other Reportable Safety Events

Type of Event	Reporting Time Period: Consent to Randomization/Allocation	Reporting Time Period: Randomization/Allocation through Protocol-specified Follow-up Period	Reporting Time Period: After the Protocol-specified Follow-up Period	Time Frame to Report Event and Follow-up Information to Sponsor:
Nonserious Adverse Event (NSAE)	Report if: - due to protocol-specified intervention - causes exclusion - participant is receiving placebo run-in or other run-in treatment	Report all	Not required	Per data entry guidelines
Serious Adverse Event (SAE)	Report if: - due to protocol-specified intervention - causes exclusion - participant is receiving placebo run-in or other run-in treatment	Report all	Report if: - drug/vaccine related. - any death until participant completion of study (Follow ongoing to outcome)	Within 24 hours of learning of event
Pregnancy/ Lactation Exposure	Report if: - due to intervention - causes exclusion	Report all	Previously reported – Follow to completion/termination; report outcome	Within 24 hours of learning of event
Event of Clinical Interest	There are no ECI for this study.			Not applicable
Cancer	Report if: - due to intervention - causes exclusion	Report all	Not required	Within 5 calendar days of learning of event
Overdose	Report if: - receiving placebo run-in or other run-in medication	Report all	Not required	Within 5 calendar days of learning of event

8.4.2 Method of Detecting AEs, SAEs, and Other Reportable Safety Events

Care will be taken not to introduce bias when detecting AEs and/or SAEs and other reportable safety events. Open-ended and nonleading verbal questioning of the participant is the preferred method to inquire about AE occurrence.

8.4.3 Follow-up of AE, SAE, and Other Reportable Safety Event Information

After the initial AE/SAE report, the investigator is required to proactively follow each participant at subsequent visits/contacts. All AEs, SAEs, and other reportable safety events, including pregnancy and exposure during breastfeeding, cancer, and overdose will be

followed until resolution, stabilization, until the event is otherwise explained, or the participant is lost to follow-up (as defined in Section 7.3). In addition, the investigator will make every attempt to follow all nonserious AEs that occur in randomized participants for outcome. Further information on follow-up procedures is given in Appendix 3.

8.4.4 Regulatory Reporting Requirements for SAE

Prompt notification (within 24 hours) by the investigator to the Sponsor of SAE is essential so that legal obligations and ethical responsibilities towards the safety of participants and the safety of a study intervention under clinical investigation are met.

The Sponsor has a legal responsibility to notify both the local regulatory authority and other regulatory agencies about the safety of a study intervention under clinical investigation. The Sponsor will comply with country-specific regulatory requirements and global laws and regulations relating to safety reporting to regulatory authorities, IRB/IECs, and investigators.

Investigator safety reports must be prepared for suspected unexpected serious adverse reactions (SUSARs) according to local regulatory requirements and Sponsor policy and forwarded to investigators as necessary.

An investigator who receives an investigator safety report describing an SAE or other specific safety information (eg, summary or listing of SAE) from the Sponsor will file it along with the IB and will notify the IRB/IEC, if appropriate according to local requirements.

8.4.5 Pregnancy and Exposure During Breastfeeding

Although pregnancy and infant exposure during breastfeeding are not considered AEs, any pregnancy or infant exposure during breastfeeding in a participant (spontaneously reported to the investigator or their designee) that occurs during the study are reportable to the Sponsor.

All reported pregnancies must be followed to the completion/termination of the pregnancy. Pregnancy outcomes of spontaneous abortion, missed abortion, benign hydatidiform mole, blighted ovum, fetal death, intrauterine death, miscarriage, and stillbirth must be reported as serious events (Important Medical Events). If the pregnancy continues to term, the outcome (health of infant) must also be reported.

8.4.6 Disease-related Events and/or Disease-related Outcomes Not Qualifying as AEs or SAEs

This is not applicable to this study.

8.4.7 Events of Clinical Interest (ECIs)

There are no events of clinical interest for this study.

8.5 Treatment of Overdose

In this study, an overdose is the administration of more than 1 dose of any individual study vaccine in any 24-hour period.

No specific information is available on the treatment of overdose.

All reports of overdose must be reported by the investigator within 5 calendar days to the Sponsor either by electronic media or paper. Electronic reporting procedures can be found in the electronic data collection (EDC) data entry guidelines. Paper reporting procedures can be found in the Investigator Trial File Binder (or equivalent).

8.6 Pharmacokinetics

PK parameters will not be evaluated in this study.

8.7 Pharmacodynamics

Pharmacodynamic parameters will not be evaluated in this study.

8.8 Future Biomedical Research Sample Collection

If the participant signs the future biomedical research consent, the following specimens will be obtained as part of future biomedical research:

- DNA for future research
- Leftover study serum after completion of immunogenicity testing stored for future research

8.9 Medical Resource Utilization and Health Economics

Medical Resource Utilization and Health Economics are not evaluated in this study.

8.10 Visit Requirements

Visit requirements are outlined in Section 1.3. Specific procedure-related details are provided in Section 8.

8.10.1 Screening

Screening procedures will be conducted at Visit 1 (Day 1) as outlined in Section 1.3.

8.10.2 Treatment Period/Vaccination Visit

Requirements during the treatment period are outlined in Section 1.3.

9 STATISTICAL ANALYSIS PLAN

This section outlines the statistical analysis strategy and procedures for the study. If, after the study has begun, but prior to any unblinding/final database lock, changes are made to hypotheses, or the statistical methods related to those hypotheses, then the protocol will be amended (consistent with International Council for Harmonisation [ICH] Guideline E-9). Changes to other non-confirmatory analyses made after the protocol has been finalized, but prior to unblinding/final database lock, will be documented in a supplemental Statistical Analysis Plan and referenced in the Clinical Study Report for the study. Post hoc exploratory analyses will be clearly identified in the Clinical Study Report.

9.1 Statistical Analysis Plan Summary

Key elements of the statistical analysis plan are summarized below; the comprehensive plan is provided in Section 9.2 to Section 9.12.

Study Design Overview	A Phase 3, Multicenter, Randomized, Double-blind, Active Comparator-controlled Study to Evaluate the Safety, Tolerability, and Immunogenicity of V114 in Healthy Adults 50 Years of Age or Older (PNEU-AGE).
Treatment Assignment	Participants will be randomly assigned in a 1:1 ratio to V114 or Prevnar 13™, respectively. Randomization will be stratified into 3 groups based on the participant's age (50 to 64 years of age, 65 to 74 years of age, and ≥ 75 years of age) at the time of randomization as described in Section 6.3.2.
Analysis Populations	Immunogenicity: Per-Protocol (PP) Safety: All Participants as Treated (APaT)
Primary Endpoint(s)	Immunogenicity: 
Serotype-specific OPA GMTs for the 15 serotypes in V114 at 30 days postvaccination (Day 30)Proportions of participants with a ≥ 4-fold rise from prevaccination (Day 1) to 30 days postvaccination (Day 30) for OPA responses for the 2 unique serotypes in V114 Safety: 
Proportion of participants with solicited injection-site AEs (redness/erythema, swelling, tenderness/pain) from Day 1 through Day 5 postvaccinationProportion of participants with solicited systemic AEs (muscle pain/myalgia, joint pain/arthralgia, headache, and tiredness/fatigue) from Day 1 through Day 14 postvaccinationProportion of participants with vaccine-related SAEs from Day 1 to Month 6 postvaccination

Key Secondary Endpoints	
Immunogenicity:
 
 • Serotype 3 OPA GMT at 30 days postvaccination (Day 30) • Proportion of participants with a ≥ 4-fold rise from prevaccination (Day 1) to 30 days postvaccination (Day 30) for serotype 3 OPA responses • Serotype-specific IgG GMCs for the 15 serotypes in V114 at 30 days postvaccination (Day 30)
Statistical Methods for Key Immunogenicity Analyses	
Immunogenicity analyses will be conducted for each of the 15 pneumococcal serotypes in V114.
 
For the first primary hypotheses, V114 will be considered noninferior to Prevnar 13™ if the lower bound of the 2-sided 95% CI of the OPA GMTs ratios (V114/Prevnar 13™) for the 13 shared serotypes is greater than 0.50.
 
For the second primary hypotheses, V114 will be considered superior to Prevnar 13™ if the lower bound of the 2-sided 95% CI of the OPA GMTs ratio (V114/Prevnar 13™) for the 2 unique serotypes contained in V114 is greater than 2.0.
 
For these hypotheses, estimation of the serotype-specific OPA GMT ratios and 95% CIs will be calculated using the constrained longitudinal data analysis (cLDA) method [Liang, K-Y and Zeger, S. L. 2000].
 
For the third primary hypotheses, V114 will be considered superior to Prevnar 13™ if the lower bound of the 2-sided 95% CI of the difference (V114 - Prevnar 13™) between proportions of participants with a ≥ 4-fold rise from prevaccination to 30 days postvaccination is greater than 0.1 for the 2 unique serotypes in V114. The between-treatment difference (V114 - Prevnar 13™) and its 95% CI will be calculated using the stratified Miettinen and Nurminen (M&N) method [Miettinen, O. and Nurminen, M. 1985].

Statistical Methods for Key Safety Analyses	
p-Values (Tier 1 endpoints) and 95% CIs (Tier 1 and Tier 2 endpoints) will be provided for between-treatment differences in the percentage of participants with events; these analyses will be performed using the M&N method [Miettinen, O. and Nurminen, M. 1985].

Interim Analyses	
To support the periodic review of safety and tolerability data across the adult V114 Phase 3 program, an external unblinded statistician will provide unblinded interim safety summaries to an independent external DMC for their review. There are no plans to conduct an interim analysis of unblinded immunogenicity data in this study. However, unblinded immunogenicity data will be made available to the DMC upon request to enable a benefit-risk assessment.

Multiplicity	
The study will be considered to have met its primary immunogenicity objectives if noninferiority is demonstrated with respect to OPA GMTs for the 13 shared serotypes and superiority is demonstrated with respect to both OPA GMTs and the proportions of participants with ≥ 4-fold rises in OPA responses for the 2 unique serotypes. Since comparisons are made individually for each of the 15 serotypes, this approach controls the 1-sided type-I error rate at 0.025, and no multiplicity adjustment is required.
 
No multiplicity adjustments will be made for the safety comparisons.

Sample Size and Power	This study will randomize approximately 600 participants into the V114 group and 600 participants into the Prevnar 13™ group. The overall power for all the primary hypotheses is >90% at an overall 1-sided 2.5% alpha-level.
------------------------------	--

9.2 Responsibility for Analyses/In-house Blinding

The statistical analysis of the data obtained from this study will be the responsibility of the Clinical Biostatistics department of the Sponsor. This study will be conducted as a double-blind study under in-house blinding procedures. The official, final database will not be unblinded until medical/scientific review has been performed, protocol deviations have been identified, and data have been declared final and complete.

The Clinical Biostatistics department will generate the randomized allocation schedule(s) for study treatment assignment. Randomization will be implemented in an IRT. Blinding issues related to the planned interim analyses are described in Section 9.7.

9.3 Hypotheses/Estimation

Objectives and hypotheses of the study are stated in Section 3.

9.4 Analysis Endpoints

Immunogenicity and safety analysis endpoints that will be evaluated for within- and/or between-intervention differences are listed below.

9.4.1 Immunogenicity Endpoints

The primary immunogenicity analysis endpoints include:

- Serotype-specific OPA GMTs at 30 days postvaccination (Day 30) for the 15 serotypes contained in V114
- Proportion of participants with a ≥ 4 -fold rise from prevaccination (Day 1) to 30 days postvaccination (Day 30) for OPA responses for the 2 unique serotypes contained in V114

The secondary immunogenicity analysis endpoints include:

- Serotype 3 OPA GMT at 30 days postvaccination (Day 30)
- Proportion of participants with a ≥ 4 -fold rise from prevaccination (Day 1) to 30 days postvaccination (Day 30) for serotype 3 OPA responses
- Serotype-specific IgG GMCs at 30 days postvaccination (Day 30)

- Serotype-specific GMFRs and proportions of participants with a ≥ 4 -fold rise from prevaccination (Day 1) to 30 days postvaccination (Day 30) for both OPA and IgG responses

9.4.2 Safety Endpoints

The safety analysis endpoints include:

- Proportion of participants with solicited injection-site AEs (redness/erythema, swelling, and tenderness/pain) from Day 1 through Day 5 postvaccination
- Proportion of participants with solicited systemic AEs (muscle pain/myalgia, joint pain/arthralgia, headache, and tiredness/fatigue) from Day 1 through Day 14 postvaccination
- Proportions of participants with the broad AE categories consisting of any AE and any vaccine-related AE from Day 1 through Day 14 postvaccination
- Proportions of participants with the broad AE categories consisting of any SAE, any vaccine-related SAE, and death from Day 1 through the duration of participation in the study. As this is a single-dose study, the broad AE category of discontinuation of study intervention due to an AE is not applicable.
- Proportion of participants with maximum temperature measurements meeting the Brighton Collaboration cut points from Day 1 through Day 5 postvaccination

9.5 Analysis Populations

9.5.1 Immunogenicity Analysis Populations

The Per-Protocol (PP) population will serve as the primary population for the analysis of immunogenicity data in this study. The PP population consists of all randomized participants without deviations from the protocol that may substantially affect the results of the immunogenicity endpoint(s). Potential deviations that may result in the exclusion of a participant from the PP population for all immunogenicity analyses include:

- Failure to receive any study vaccine at Visit 1 (Day 1)
- Failure to receive correct clinical material as per randomization schedule at Visit 1 (Day 1) (ie, participants who were cross-treated)
- Receipt of prohibited medication or prohibited vaccine prior to study vaccination

Additional potential deviations that may result in the exclusion of a participant's measurement from a specific time point assessment in the PP population for immunogenicity analyses include:

- Receipt of prohibited medication or prohibited vaccine prior to a blood sample collection
- Collection of blood sample outside of the prespecified window (as described in Section 1.3)

The final determination on protocol deviations, and thereby the composition of the PP population, will be made prior to the final unblinding of the database. Participants will be included in the vaccination group to which they are randomized for the analysis of immunogenicity data using the PP population.

A supportive analysis using the Full Analysis Set (FAS) population will also be performed for the primary immunogenicity endpoints. The FAS population consists of all randomized participants who received at least 1 vaccination and have at least 1 serology result. Participants will be included in the vaccination group to which they are randomized for the analysis of immunogenicity data using the FAS population.

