5.2 Exclusion Criteria

The participant must be excluded from the study if the participant:

Medical Conditions

1. Has a history of IPD (positive blood culture, positive cerebrospinal fluid culture, or positive culture at another sterile site) or known history of other culture-positive pneumococcal disease within 3 years of Visit 1 (Day 1).
2. Has a known hypersensitivity to any component of pneumococcal polysaccharide vaccine, PCV, or any diphtheria toxoid-containing vaccine.
3. Has a known or suspected impairment of immunological function including, but not limited to, a history of congenital or acquired immunodeficiency, documented human immunodeficiency virus (HIV) infection, functional or anatomic asplenia, or history of autoimmune disease (including but not limited to the autoimmune conditions outlined in the Investigator Trial File Binder for this study).

4. Has a coagulation disorder contraindicating intramuscular vaccinations.
5. *Had a recent febrile illness (defined as oral or tympanic temperature $\geq 100.4^{\circ}\text{F}$ [$\geq 38.0^{\circ}\text{C}$] or axillary or temporal temperature $\geq 99.4^{\circ}\text{F}$ [$\geq 37.4^{\circ}\text{C}$]) or received antibiotic therapy for any acute illness occurring within 72 hours before receipt of study vaccine.
6. Has a history of malignancy ≤ 5 years prior to signing informed consent, except for adequately treated basal cell or squamous cell skin cancer or in situ cervical cancer.
7. A WOCBP who has a positive urine or serum pregnancy test before the first vaccination at Visit 1 (Day 1).

Prior/Concomitant Therapy

8. Has received any pneumococcal vaccine or is expected to receive any pneumococcal vaccine during the study outside of the protocol.
9. Has received systemic corticosteroids (prednisone equivalent of ≥ 20 mg/day) for ≥ 14 consecutive days and has not completed intervention at least 30 days before study entry.
10. Has received systemic corticosteroids exceeding physiologic replacement doses (approximately 5 mg/day prednisone equivalent) within 14 days before vaccination. **(Note:** Topical, ophthalmic, intra-articular or soft-tissue [eg, bursa, tendon steroid injections], and inhaled/nebulized steroids are permitted).
11. Is receiving immunosuppressive therapy, including chemotherapeutic agents used to treat cancer or other conditions, and interventions associated with organ or bone marrow transplantation, or autoimmune disease.

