6.5 Concomitant Therapy

Medications or vaccinations specifically prohibited in the exclusion criteria are not allowed during the ongoing study (see Section 5.2). If there is a clinical indication for any medications or vaccinations specifically prohibited, discontinuation from study intervention may be required. The investigator should discuss any questions regarding this with the Sponsor Clinical Director. The final decision on any supportive therapy or vaccination rests with the investigator and/or the participant's primary physician. However, the decision to continue the participant on study intervention requires the mutual agreement of the investigator, the Sponsor, and the participant.

Listed below (items 1 to 4) are specific restrictions for concomitant therapy or vaccination during the course of the study:

1. Any administration of a non-study pneumococcal vaccine is prohibited during the study.
2. Live and non-live vaccines may only be administered prior to or following the receipt of study vaccine according to the time frames specified in Exclusion Criteria (Section 5.2). **Exception:** Inactivated influenza vaccine may be administered but must be given at least 7 days before receipt of any study vaccine or at least 15 days after receipt of any study vaccine.
3. Participants should not receive systemic corticosteroids (prednisone equivalent of ≥ 20 mg/day for ≥ 14 consecutive days) starting from 30 days prior to through 30 days following vaccination.
4. Participants should not receive systemic corticosteroids exceeding physiologic replacement doses (prednisone equivalent dose > 5 mg/day) within 14 days before any vaccination.

Note: Topical, ophthalmic, intra-articular or soft-tissue (eg, bursa, tendon steroid injections), and inhaled/nebulized steroids are permitted.

Any deviation from the above requires consultation between the investigator and the Sponsor and written documentation of the collaborative decision on participant management.

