8.2.1 Multiplex Opsonophagocytic Assay (MOPA)

The MOPA, developed and published by [name] (Director of the US World Health Organization pneumococcal serology reference laboratory and National Institutes of Health pneumococcal reference laboratories), is a multiplexed OPA assay capable of measuring 4 serotypes at a time against a total of 16 serotypes of pneumococci [Burton, Robert L. and Nahm, Moon H. 2006]. The OPA is an antibody-mediated killing assay that measures the ability of human serum to kill *S. pneumoniae* serotypes with the help of complement and phagocytic effector cells. The ability of the assay to simultaneously test 4 serotypes/run reduces the amount of serum needed for testing. The assay readout is the opsonization index, which is the reciprocal of the highest dilution that gives $\geq 50\%$ bacterial killing, as determined by comparison to assay background controls. MSD has developed and optimized the MOPA in a high throughput micro-colony platform. The MOPA assay for all 15 V114 serotypes has undergone validation. The validation study evaluated various performance parameters of the assay including precision, relative accuracy/dilutional linearity, and specificity. The validation results were evaluated against prespecified acceptance criteria for each of the parameters.

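### Does the lack of an antibiotic rule before the Day 30 blood draw bias the per-protocol OPA comparisons?

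*Combined protocol and SAP*

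**What the plan says.** **Before vaccination.** Section 5.2, item 5, excludes anyone who had a recent febrile illness "or received antibiotic therapy for any acute illness occurring within 72 hours before receipt of study vaccine". The item carries an asterisk, so the Day 1 visit may be rescheduled.

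**During the study.** Section 6.5 opens with a general rule: "Medications or vaccinations specifically prohibited in the exclusion criteria are not allowed during the ongoing study (see Section 5.2". It then continues: "Listed below (items 1 to 4) are specific restrictions for concomitant therapy or vaccination during the course of the study". The four items cover pneumococcal vaccines, other vaccines and two corticosteroid rules. Antibiotics are not named.

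**Per-protocol population.** Section 9.5.1 removes deviations that could materially affect the immunogenicity results. Among the potential reasons for dropping one time point it gives "Receipt of prohibited medication or prohibited vaccine prior to a blood sample collection". The reasons are worded as ones that may lead to exclusion, and the list is introduced as inclusive. The final decision comes before the database is unblinded.

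**Assay.** Section 8.2.1 states: "The OPA is an antibody-mediated killing assay that measures the ability of human serum to kill" pneumococci with complement and phagocytic cells. The titre is the reciprocal of the highest dilution giving at least 50% killing, "as determined by comparison to assay background controls". Residual antibiotic is not mentioned.

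**Medication records.** The Schedule of Activities includes a medication review at Visit 2, and Section 8.1.5.2 has the site record medication taken during the study. Participant entries in the electronic report card run only to Day 14 (Section 8.3.4).

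**The concern.** The Day 1 sample is drawn immediately before vaccination, so the 72-hour rule in item 5 also covers that sample. The Day 30 sample has no such cover. If antibiotic in the serum killed bacteria in the assay, some Day 30 titres would be too high for reasons unrelated to either vaccine. If such use is not a prohibited medication, the PP rule would not remove those results. The supportive Full Analysis Set (FAS) analysis would keep them as well, so comparing the two populations would reveal nothing.

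The stake is greatest for H1. Killing unrelated to vaccine could make the arms look more alike, which for a noninferiority test is the direction that makes a false claim easier. For serotypes 22F and 33F, it could also create spurious 4-fold risers in the comparator arm.

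**Working it through.** **1. Is such use prohibited?** Two readings are available.

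- Narrow: item 5 bars only use in the 72 hours before vaccination, so an antibiotic taken just before Visit 2 is no deviation.
- Broad: the opening sentence of Section 6.5 extends the exclusion-criteria prohibitions through the study. Antibiotic therapy for acute illness is then a prohibited medication, and Section 9.5.1 can remove the Day 30 value.

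The text does not choose between them, so it does not establish that PP keeps these sera.

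**2. The plan's own power.** Inputs from Section 9.9.1: 540 evaluable per arm, lowest assumed shared-serotype ratio 0.78, margin 0.50, and SDs of ln titre up to 2.24 (V114) and 2.25 (comparator). The one-sided alpha is 0.025.

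- Root mean square SD = 2.245; SE = 2.245 × √(2/540) = 0.1366
- ln(0.78/0.50) = 0.4447
- Power = Φ(0.4447/0.1366 − 1.96) = 90.2%

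At the smallest SDs (1.33 and 1.37; root mean square 1.35) power is 99.97%. Both agree with the stated figure of more than 90%. The joint figure over all hypotheses cannot be reproduced, because the inputs are given only as ranges.

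**3. What would affected sera do to the GMT ratio?** Let f be the share of Day 30 sera affected, equal in both arms. The documents give no value, so f is an assumption, shown from 0.5% to 10%. The answer depends on the form of the effect.

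*Model A: every affected titre is raised by the same amount k in ln units.* Each arm's mean rises by f × k, and the difference cancels:

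- ln ratio: unchanged
- Variance: SD² + f(1−f)k²
- Error at a true ratio of 0.50: still 2.5%
- Example with f = 1%, k = 4, SD 2.245: variance = 5.040 + 0.0099 × 16 = 5.198; SE = 0.1388; power at 0.78 = Φ(0.4447/0.1388 − 1.96) = 89.3%, against 90.2%

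This model costs a little power and adds no false noninferiority claims.

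*Model B: affected sera in both arms take one common titre, c ln units above the mean.*

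- ln ratio: multiplied by (1−f)
- Variance: (1−f)SD² + f(1−f)c², with c = ln 4 or ln 16
- Error at a true ratio of 0.50: 1 − Φ(1.96 − f × ln 2/SE)

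| f | Ratio 0.50 becomes | Ratio 0.78 becomes | One-sided error at true 0.50 (SD 1.35 to 2.245) |
|---|---|---|---|
| 0.5% | 0.502 | 0.781 | 2.7–2.8% |
| 1% | 0.503 | 0.782 | 2.8–3.0% |
| 2% | 0.507 | 0.784 | 3.2–3.7% |
| 3% | 0.511 | 0.786 | 3.5–4.4% |
| 5% | 0.518 | 0.790 | 4.4–6.2% |
| 10% | 0.536 | 0.800 | 7.2–13.3% |

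The pull towards 1 therefore belongs to Model B alone. At f = 2% about 11 of 540 sera per arm are affected (540 × 0.02 = 10.8).

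**4. The superiority tests.** Under Model B a ratio at the H2 bound of 2.0 moves to 2.0^0.99 = 1.986 at f = 1%, and one at the H4 bound of 1.2 moves to 1.198. Both moves make the test harder to pass. For H3, suppose every affected serum becomes a 4-fold riser. Each proportion p becomes p + f(1−p), so the difference is multiplied by (1−f): 0.30 becomes 0.294 at f = 2%. A true difference at the bound of 0.1 falls below it. Spurious risers in the comparator arm thus make H3 conservative. For H5, a true difference of 0 stays at 0.

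**The case for a change.** The strongest case for acting is that neither reading of Section 6.5 gives a clean rule. Read narrowly, a result from a participant taking antibiotics at the draw stays in PP. Read broadly, any antibiotic course for acute illness after vaccination counts. Section 9.5.1 sets no window before the sample, so a course that ended weeks earlier could remove a valid result. One sentence with a defined window would settle this, and the model for OPA GMTs already accommodates a missing Day 30 value.

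That ambiguity stands, as does the point that FAS would not expose the problem if PP kept the sera. Within-group fold rises would also be affected even under Model A, where the GMT ratio is not.

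Three things limit what follows. The documents nowhere say that residual antibiotic raises this readout. Item 5 pairs antibiotics with recent fever and ties both to vaccination, so it reads equally well as deferral for acute illness, and it cannot be taken as evidence of an assay concern. Finally, a 72-hour rule at Day 30 needs medication dates that participants do not enter after Day 14. The Visit 2 review may supply them, but the documents do not say how precisely.

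**Conclusion.** This is a missing detail that analysts can fill. Whether antibiotic use shortly before the Day 30 draw is a time-point deviation for OPA can be decided in the deviation review that Section 9.5.1 already places before unblinding, using the Visit 2 medication review. Following the plan as written still gives sound conclusions.

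Any bias in favour of V114 is confined to H1. It requires all of the following: residual antibiotic alters the assay despite the background controls; affected sera read at a common level in both arms; PP review leaves them in; and a serotype's true ratio is near 0.50. The plan's lowest assumed ratio is 0.78. Under those conditions the increase is about 0.3 to 0.5 percentage points at an assumed 1% of sera (2.8–3.0% against 2.5%). It becomes material only at a prevalence for which the documents give no support: 4.4–6.2% at 5% of sera, and 7.2–13.3% at 10%. If the affected share differed between arms, the ratio could move in either direction; nothing in the plan suggests a difference between randomised, blinded arms.
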